10.3. Appendix 3: Assessment Windows

All assessments/events (including those from planned, unscheduled and withdrawal visits) will be assigned to assessment windows/analysis visits according to actual dates of collection rather than the nominal visit labels recorded on the eCRF or in the laboratory database.

For parameters which are not scheduled to be assessed at a particular visit, all-inclusive assessment windows will still be used; however, data displays summarizing measurements by visit will only report visits in which the parameter is a planned collection according to [Appendix 2: Schedule of Activities](#).

Note: Prior to visit slotting, assessments are first assigned to a study period according to Table 5.

10.3.1. Definitions of Assessments Windows

Table 1 Assessment Windows for Screening and OLI Period Data

Parameter	Analysis Window	Target Period Day	Analysis Timepoint
Assessments assigned to Period=Screening or OLI (per Table 5)			
Vital signs, Labs, ECG, Weight, Pregnancy Test, Drug/Alcohol Screen, Coagulation Tests	OLI Period Day <1	The day of earliest record	Screening
PK, Vital Signs, Labs, ECG, Pregnancy Test, Drug/Alcohol Screen	OLI Period Day = 1	1	Day 1
PK, Vital Signs, Labs	OLI Period Day = 2	2	Day 2
Vital Signs, Labs, Pregnancy Test	$3 \leq \text{OLI Period Day} \leq 21$	14	Day 14
PK	$13 \leq \text{OLI Period Day} \leq 15$	14	Day 14
ECG	$2 \leq \text{OLI Period Day}$	29	Day 29
Vital Signs, Labs, Pregnancy Test	$22 \leq \text{OLI Period Day}$	29	Day 29
PK	$28 \leq \text{OLI Period Day} \leq 30$	29	Day 29
Coagulation Tests	$1 \leq \text{OLI Period Day}$	29	Day 29
Vital signs, Labs, ECG, Weight, PK, Coagulation Tests, Pregnancy Test	OLI Period Day > [(OLI Stop Date – OLI Start Date + 1) + 1]		Washout
Vital signs, Labs, ECG	Date of Assessment = Date of Injection 1		Injection 1 Day 1
If none of the above			Day X, where X=OLI period day

Note: if a record falls within more than one analysis window then the record will be assigned to the latest applicable analysis timepoint (e.g., if a record falls within the analysis window for Day 14 and Washout, then the record will be assigned to Washout; if a record falls within the analysis window for Washout and Injection 1 Day 1, then the record will be assigned to Injection 1 Day 1).

Table 2 Assessment Windows for Part 1 Injection and Follow Up Phase Data

Parameter	Analysis Window	Target Period Day	Analysis Timepoint
Assessments assigned to Period=Injection 1 (per Table 5)			
PK, Vital Signs, Labs, ECG, NRS, Pregnancy Test, Brief Physical Exam, HIV Test	Injection 1 Period Day = 1	1	Day 1
PK, Vital Signs, NRS	Injection 1 Period Day = 2	2	Day 2
Brief Physical Exam	$2 \leq \text{Injection 1 Period Day} \leq 5$	2	Day 2
Cohort 4h: ECG	Injection 1 Period Day = 2	2	Day 2
Vital Signs	$3 \leq \text{Injection 1 Period Day} \leq 4$	3	Day 3
Cohort 4b: Vital Signs	Injection 1 Period Day = 3	3	Day 3
Cohort 4h: ECG	Injection 1 Period Day = 3	3	Day 3
PK	Injection 1 Period Day = 3	3	Day 3
Cohort 4b: PK, Vital Signs	Injection 1 Period Day = 4	4	Day 4
Cohort 4h: PK, ECG	Injection 1 Period Day = 4	4	Day 4
PK, Vital Signs, NRS	Injection 1 Period Day = 5	5	Day 5
Cohort 4h: ECG	Injection 1 Period Day = 5	5	Day 5
PK, Vital Signs	Injection 1 Period Day = 6	6	Day 6
Cohort 4h: ECG	Injection 1 Period Day = 6	6	Day 6
PK, Vital Signs	Injection 1 Period Day = 7	7	Day 7
Cohort 4h: ECG	Injection 1 Period Day = 7	7	Day 7
NRS, PIN, PK	Injection 1 Period Day = 8	8	Day 8
Cohort 4h: ECG	$8 \leq \text{Injection 1 Period Day} \leq 9$	8	Day 8
Vital Signs	$8 \leq \text{Injection 1 Period Day} \leq 9$	8	Day 8
Labs	$2 \leq \text{Injection 1 Period Day} \leq 11$	8	Day 8
Brief Physical Exam	$6 \leq \text{Injection 1 Period Day} \leq 18$	8	Day 8
PK	Injection 1 Period Day = 10	10	Day 10
Vital Signs	$10 \leq \text{Injection 1 Period Day} \leq 12$	10	Day 10
Cohort 4h: ECG	$10 \leq \text{Injection 1 Period Day}$	10	Day 10
PK, Vital Signs	$13 \leq \text{Injection 1 Period Day} \leq 15$	14	Day 14
Labs	$12 \leq \text{Injection 1 Period Day} \leq 21$	14	Day 14
Pregnancy Test	$2 \leq \text{Injection 1 Period Day} \leq 21$	14	Day 14
Vital Signs	$16 \leq \text{Injection 1 Period Day} \leq 19$	17	Day 17
PK	$16 \leq \text{Injection 1 Period Day} \leq 18$	17	Day 17
Vital Signs	$20 \leq \text{Injection 1 Period Day} \leq 25$	22	Day 22
PK	$21 \leq \text{Injection 1 Period Day} \leq 23$	22	Day 22
Weight	$15 \leq \text{Injection 1 Period Day}$	28	Week 4
Vital Signs	$26 \leq \text{Injection 1 Period Day}$	28	Week 4
PK	$25 \leq \text{Injection 1 Period Day} \leq 31$	28	Week 4
Labs	$22 \leq \text{Injection 1 Period Day}$	28	Week 4
Pregnancy Test	$22 \leq \text{Injection 1 Period Day}$	28	Week 4
Brief Physical Exam	$19 \leq \text{Injection 1 Period Day}$	28	Week 4
HIV Test	$2 \leq \text{Injection 1 Period Day}$	28	Week 4

Parameter	Analysis Window	Target Period Day	Analysis Timepoint
	If none of the above		Day X, where X=Injection 1 Period Day
Assessments assigned to Period=Injection 2 (per Table 5)			
PK, Vital Signs, Labs, ECG, NRS, Pregnancy Test, Brief Physical Exam, HIV Test,	Injection 2 Period Day = 1	1	Day 1
PK, Vital Signs, NRS	Injection 2 Period Day = 2	2	Day 2
Brief Physical Exam	$2 \leq \text{Injection 2 Period Day} \leq 5$	2	Day 2
Vital Signs	$3 \leq \text{Injection 2 Period Day} \leq 4$	3	Day 3
Cohort 4b: Vital Signs	Injection 2 Period Day = 3	3	Day 3
PK	Injection 2 Period Day = 3	3	Day 3
Cohort 4b: PK, Vital Signs	Injection 1 Period Day = 4	4	Day 4
PK, Vital Signs, NRS	Injection 2 Period Day = 5	5	Day 5
PK, Vital Signs	Injection 2 Period Day = 6	6	Day 6
PK, Vital Signs	Injection 2 Period Day = 7	7	Day 7
NRS, PIN, PK	Injection 2 Period Day = 8	8	Day 8
Vital Signs	$8 \leq \text{Injection 2 Period Day} \leq 9$	8	Day 8
Labs	$2 \leq \text{Injection 2 Period Day} \leq 11$	8	Day 8
Vital Signs	$10 \leq \text{Injection 2 Period Day} \leq 12$	10	Day 10
PK	Injection 2 Period Day = 10	10	Day 10
PK, Vital Signs	$13 \leq \text{Injection 2 Period Day} \leq 15$	14	Day 14
Labs	$12 \leq \text{Injection 2 Period Day} \leq 21$	14	Day 14
Pregnancy Test	$2 \leq \text{Injection 2 Period Day} \leq 21$	14	Day 14
Vital Signs	$16 \leq \text{Injection 2 Period Day} \leq 19$	17	Day 17
PK	$16 \leq \text{Injection 2 Period Day} \leq 18$	17	Day 17
Vital Signs	$20 \leq \text{Injection 2 Period Day} \leq 25$	22	Day 22
PK	$21 \leq \text{Injection 2 Period Day} \leq 23$	22	Day 22
Weight	$15 \leq \text{Injection 2 Period Day}$	28	Week 4
Vital Signs	$26 \leq \text{Injection 2 Period Day}$	28	Week 4
PK	$25 \leq \text{Injection 2 Period Day} \leq 31$	28	Week 4
Labs	$22 \leq \text{Injection 2 Period Day}$	28	Week 4
Pregnancy Test	$22 \leq \text{Injection 2 Period Day}$	28	Week 4
Brief Physical Exam	$19 \leq \text{Injection 2 Period Day}$	28	Week 4
HIV Test	$2 \leq \text{Injection 2 Period Day}$	28	Week 4
	If none of the above		Day X, where X=Injection 2 Period Day
Assessments assigned to Period=Follow-up (per Table 5)			
Vital Signs, Labs, Pregnancy Test, Brief Physical Exam	(Date of Nominal Follow-up Week 4 Visit – Date of Final CAB Injection ^a + 1) < Follow-up Period Day ≤ 70	56	Week 8
PK	$53 \leq \text{Follow-up Period Day} \leq 59$	56	Week 8
Vital Signs, Labs, Pregnancy Test, Brief Physical Exam	$71 \leq \text{Follow-up Period Day} \leq 168$	84	Week 12
PK	$81 \leq \text{Follow-up Period Day} \leq 87$	84	Week 12

Parameter	Analysis Window	Target Period Day	Analysis Timepoint
PK	$137 \leq \text{Follow-up Period Day} \leq 143$	140	Week 20
Weight	$113 (\text{week } 16) \leq \text{Follow-up Period Day} \leq 280 (\text{week } 40)$	196	Week 28
PK	$193 \leq \text{Follow-up Period Day} \leq 199$	196	Week 28
Vital Signs, Labs, Pregnancy Test, Brief Physical Exam	$169 \leq \text{Follow-up Period Day} \leq 280 (\text{week } 40)$	252	Week 36
PK	$249 \leq \text{Follow-up Period Day} \leq 255$	252	Week 36
Vital Signs, Labs, Pregnancy Test, Brief Physical Exam	$281 \leq \text{Follow-up Period Day} \leq 336 (\text{week } 48)$	308	Week 44
PK	$305 \leq \text{Follow-up Period Day} \leq 311$	308	Week 44
Weight	$281 \leq \text{Follow-up Period Day}$	364	Week 52
Vital Signs, Labs, Pregnancy Test, Brief Physical Exam	$337 \leq \text{Follow-up Period Day}$	364	Week 52
PK	$361 \leq \text{Follow-up Period Day} \leq 367$	364	Week 52
If none of the above			Day X, where X=Follow-up Period Day
NOTES: 
 • OLI Day, Injection 1 Day, Injection 2 Day and Follow-up Day are defined in Section 10.6.1. 			

Table 3 Assessment Windows for Part 2 Injection and Follow-up Phase Data

Parameter	Analysis Window	Target Period Day	Analysis Timepoint
Assessments assigned to Period=Injection 1 (per Table 5)			
PK, Vital Signs, Labs, ECG, NRS, Weight, Pregnancy Test, Brief Physical Exam, HIV Test, Coagulation Tests	Injection 1 Period Day = 1	1	Day 1
PK, Vital Signs, Labs, ECG, NRS	Injection 1 Period Day = 2	2	Day 2
Brief Physical Exam	$2 \leq \text{Injection 1 Period Day} \leq 4$	2	Day 2
Vital Signs, Labs, ECG	$3 \leq \text{Injection 1 Period Day} \leq 4$	3	Day 3
PK	Injection 1 Period Day = 3	3	Day 3
PK, Vital Signs, ECG, NRS	Injection 1 Period Day = 5	5	Day 5
Labs	$5 \leq \text{Injection 1 Period Day} \leq 6$	5	Day 5
PK, Vital Signs, ECG	Injection 1 Period Day = 6	6	Day 6
Brief Physical Exam	$5 \leq \text{Injection 1 Period Day} \leq 8$	6	Day 6
PK, Vital Signs, ECG	Injection 1 Period Day = 7	7	Day 7
Labs	$7 \leq \text{Injection 1 Period Day} \leq 8$	7	Day 7
PK, NRS, PIN	Injection 1 Period Day = 8	8	Day 8
Vital Signs, ECG	$8 \leq \text{Injection 1 Period Day} \leq 9$	8	Day 8
Labs	$9 \leq \text{Injection 1 Period Day} \leq 12$	10	Day 10
Vital Signs, ECG	$10 \leq \text{Injection 1 Period Day} \leq 12$	10	Day 10

Parameter	Analysis Window	Target Period Day	Analysis Timepoint
PK	Injection 1 Period Day = 10	10	Day 10
Brief Physical Exam	$9 \leq \text{Injection 1 Period Day} \leq 16$	10	Day 10
PK, Vital Signs	$13 \leq \text{Injection 1 Period Day} \leq 15$	14	Day 14
Labs	$13 \leq \text{Injection 1 Period Day} \leq 18$	14	Day 14
Pregnancy Test	$2 \leq \text{Injection 1 Period Day} \leq 28$	14	Day 14
Vital Signs	$16 \leq \text{Injection 1 Period Day} \leq 19$	17	Day 17
PK	$16 \leq \text{Injection 1 Period Day} \leq 18$	17	Day 17
Labs	$19 \leq \text{Injection 1 Period Day} \leq 25$	22	Day 22
Vital Signs	$20 \leq \text{Injection 1 Period Day} \leq 25$	22	Day 22
PK	$21 \leq \text{Injection 1 Period Day} \leq 23$	22	Day 22
Brief Physical Exam	$17 \leq \text{Injection 1 Period Day} \leq 32$	22	Day 22
Coagulation Tests	$2 \leq \text{Injection 1 Period Day}$	22	Day 22
Labs	$26 \leq \text{Injection 1 Period Day} \leq 42$	28	Week 4
Vital Signs	$26 \leq \text{Injection 1 Period Day} \leq 35$	28	Week 4
PK	$25 \leq \text{Injection 1 Period Day} \leq 31$	28	Week 4
Vital Signs	$36 \leq \text{Injection 1 Period Day} \leq 49$	42	Week 6
PK	$41 \leq \text{Injection 1 Period Day} \leq 43$	42	Week 6
Pregnancy Test	$29 \leq \text{Injection 1 Period Day} \leq 63$	42	Week 6
Brief Physical Exam	$33 \leq \text{Injection 1 Period Day} \leq 63$	42	Week 6
Labs	$43 \leq \text{Injection 1 Period Day} \leq 70$	56	Week 8
Vital Signs	$50 \leq \text{Injection 1 Period Day} \leq 63$	56	Week 8
PK	$55 \leq \text{Injection 1 Period Day} \leq 57$	56	Week 8
Vital Signs	$64 \leq \text{Injection 1 Period Day} \leq 77$	70	Week 10
PK	$69 \leq \text{Injection 1 Period Day} \leq 71$	70	Week 10
Weight, HIV Test	$2 \leq \text{Injection 1 Period Day}$	84	Week 12
Vital Signs	$78 \leq \text{Injection 1 Period Day}$	84	Week 12
PK	$81 \leq \text{Injection 1 Period Day} \leq 87$	84	Week 12
Labs	$71 \leq \text{Injection 1 Period Day}$	84	Week 12
Pregnancy Test, Brief Physical Exam	$64 \leq \text{Injection 1 Period Day}$	84	Week 12
If none of the above			Day X, where $X = \text{Injection 1 Period Day}$
Assessments assigned to Period=Injection 2 (per Table 5)			
PK, Vital Signs, Labs, ECG, NRS, Weight, Pregnancy Test, Brief Physical Exam, HIV Test, Coagulation Tests	Injection 2 Period Day = 1	1	Day 1
PK, Vital Signs, Labs, ECG, NRS	Injection 2 Period Day = 2	2	Day 2
Brief Physical Exam	$2 \leq \text{Injection 2 Period Day} \leq 4$	2	Day 2
Vital Signs, Labs, ECG	$3 \leq \text{Injection 2 Period Day} \leq 4$	3	Day 3
PK	Injection 2 Period Day = 3	3	Day 3
PK, Vital Signs, ECG, NRS	Injection 2 Period Day = 5	5	Day 5
Labs	$5 \leq \text{Injection 2 Period Day} \leq 6$	5	Day 5
PK, Vital Signs, ECG	Injection 2 Period Day = 6	6	Day 6
Brief Physical Exam	$5 \leq \text{Injection 2 Period Day} \leq 8$	6	Day 6

Parameter	Analysis Window	Target Period Day	Analysis Timepoint
PK, Vital Signs, ECG	Injection 2 Period Day = 7	7	Day 7
Labs	$7 \leq \text{Injection 2 Period Day} \leq 8$	7	Day 7
PK, NRS, PIN	Injection 2 Period Day = 8	8	Day 8
Vital Signs, ECG	$8 \leq \text{Injection 2 Period Day} \leq 9$	8	Day 8
Labs	$9 \leq \text{Injection 2 Period Day} \leq 12$	10	Day 10
Vital Signs, ECG	$10 \leq \text{Injection 2 Period Day} \leq 12$	10	Day 10
PK	Injection 2 Period Day = 10	10	Day 10
Brief Physical Exam	$9 \leq \text{Injection 2 Period Day} \leq 16$	10	Day 10
PK, Vital Signs	$13 \leq \text{Injection 2 Period Day} \leq 15$	14	Day 14
Labs	$13 \leq \text{Injection 2 Period Day} \leq 18$	14	Day 14
Pregnancy Test	$2 \leq \text{Injection 2 Period Day} \leq 28$	14	Day 14
Vital Signs	$16 \leq \text{Injection 2 Period Day} \leq 19$	17	Day 17
PK	$16 \leq \text{Injection 2 Period Day} \leq 18$	17	Day 17
Labs	$19 \leq \text{Injection 2 Period Day} \leq 25$	22	Day 22
Vital Signs	$20 \leq \text{Injection 2 Period Day} \leq 25$	22	Day 22
PK	$21 \leq \text{Injection 2 Period Day} \leq 23$	22	Day 22
Brief Physical Exam	$17 \leq \text{Injection 2 Period Day} \leq 32$	22	Day 22
Coagulation Tests	$2 \leq \text{Injection 2 Period Day}$	22	Day 22
Labs	$26 \leq \text{Injection 2 Period Day} \leq 42$	28	Week 4
Vital Signs	$26 \leq \text{Injection 2 Period Day} \leq 35$	28	Week 4
PK	$27 \leq \text{Injection 2 Period Day} \leq 29$	28	Week 4
Vital Signs	$36 \leq \text{Injection 2 Period Day} \leq 49$	42	Week 6
PK	$41 \leq \text{Injection 2 Period Day} \leq 43$	42	Week 6
Pregnancy Test	$29 \leq \text{Injection 2 Period Day} \leq 63$	42	Week 6
Brief Physical Exam	$33 \leq \text{Injection 2 Period Day} \leq 63$	42	Week 6
Labs	$43 \leq \text{Injection 2 Period Day} \leq 70$	56	Week 8
Vital Signs	$50 \leq \text{Injection 2 Period Day} \leq 63$	56	Week 8
PK	$55 \leq \text{Injection 2 Period Day} \leq 57$	56	Week 8
Vital Signs	$64 \leq \text{Injection 2 Period Day} \leq 77$	70	Week 10
PK	$69 \leq \text{Injection 2 Period Day} \leq 71$	70	Week 10
Weight, HIV Test	$2 \leq \text{Injection 2 Period Day}$	84	Week 12
Vital Signs	$78 \leq \text{Injection 2 Period Day}$	84	Week 12
PK	$81 \leq \text{Injection 2 Period Day} \leq 87$	84	Week 12
Labs	$71 \leq \text{Injection 2 Period Day}$	84	Week 12
Pregnancy Test, Brief Physical Exam	$64 \leq \text{Injection 2 Period Day}$	84	Week 12
If none of the above			Day X, where $X = \text{Injection 2 Period Day}$
Assessments assigned to Period=Follow-up (per Table 5)			
Vital Signs, Labs, Pregnancy Test	(Date of Nominal Follow-up Week 12 Visit – Date of Final CAB Injection ^a + 1) < Follow-up Period Day ≤ 224 (week 32)	168	Week 24

Parameter	Analysis Window	Target Period Day	Analysis Timepoint
Weight	(Date of Nominal Follow-up Week 12 Visit – Date of Final CAB Injection ^a + 1) < Follow-up Period Day ≤ 266 (week 38)	168	Week 24
PK	$165 \leq \text{Follow-up Period Day} \leq 171$	168	Week 24
Vital Signs, Labs, Pregnancy Test	$225 \leq \text{Follow-up Period Day} \leq 322$ (week 46)	280	Week 40
PK	$277 \leq \text{Follow-up Period Day} \leq 283$	280	Week 40
Weight	$267 \leq \text{Follow-up Period Day}$	364	Week 52
Vital Signs, Labs, Pregnancy Test	$323 \leq \text{Follow-up Period Day}$	364	Week 52
PK	$361 \leq \text{Follow-up Period Day} \leq 367$	364	Week 52
If none of the above			Day X, where X=Follow-up Period Day
NOTES: 
 OLI Period Day, Injection 1 Period Day, Injection 2 Period Day and Follow-up Period Day are defined in Section 10.6.1. 			

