6. AE assessment will include a brief, symptom-directed physical exam as needed.
7. A total of 25 PK samples will be collected through the injection phase and Follow-up.
8. Urine or plasma pregnancy testing to be performed pre-injection where relevant
9. HIV antibody test (either a laboratory or point of care test).
10. See Section [8.2.6](#).
11. Plasma samples (K3-EDTA) for optional rHuPH20 immunogenicity analysis at pre-dose, Day 14 and Day 28. Analysis will be event-driven, (e.g. only if there are safety observations suggestive of an immune-mediated event).
12. Participants may be discharged from the clinic between Injection Day 5 and Injection Day 8. If participants are discharged prior to Injection Day 8, they would return to the clinic for assessments on the days specified in the SoA. **Where SARS-CoV-2 is circulating in the community**, participants should have a SARS-CoV-2 test on the day they are being discharged from the clinic.
13. No urinalysis needs to be performed on Days 3 and 5.

1.3.5. CAB 400 mg/mL or 200 mg/mL LA Injection Phase and Follow- up: Part 2 Cohorts 5 and 6

		Injection Phase																Follow-up Phase						
Injection 1 ¹⁰	Within 7 and/or 5 days of admission to the clinic ³	Inj 1 Day 1				Inj 1 Day 2	Inj 1 Day 3	Inj 1 Day 5	Inj 1 Day 6	Inj 1 Day 7	Inj 1 Day 8	Inj 1 Day 10	Inj 1 Day 14	Inj 1 Day 17	Inj 1 Day 22	Inj 1 Week 4	Inj 1 Week 6	Inj 1 Week 8	Inj 1 Week 10	Inj 1 Week 12 - proceed to Injection 2 Day 1	Follow-up post last injection			
Injection 2	Within 7 and/or 5 days of admission to the clinic ³	Inj 2 Day 1				Inj 2 Day 2	Inj 2 Day 3	Inj 2 Day 5	Inj 2 Day 6	Inj 2 Day 7	Inj 2 Day 8	Inj 2 Day 10	Inj 2 Day 14	Inj 2 Day 17	Inj 2 Day 22	Inj 2 Week 4	Inj 2 Week 6	Inj 2 Week 8	Inj 2 Week 10	Inj 2 Week 12 - proceed to follow-up	Week 12	Week 24	Week 40	Week 52/EW ¹
		Pre-dose ²	1 h	2 h	8 h	24 h																		
Permitted window for PK collection		Within 1 h prior to dosing	±15 min	±30 min	±1 h	±2 h	±2 h	±2 h	±2 h	±2 h	±2 h	±1 day	±1 day	±1 day	±1 day	±1 day	±1 day	±1 day	±1 day		±3 days	±3 days	±3 days	±3 days
Interim Medical / Medication/ Drug / Alcohol History		X																						
Pregnancy Test ^{3,8}		X										X					X				X	X	X	X
Triplicate 12-Lead ECG		X		X		X	X	X	X	X	X	X												

		Injection Phase																	Follow-up Phase			

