Section 8.1.5.1 Statistical Methodology Specification	• Clarified plan to perform PK pairwise comparisons between cohorts receiving the same dose. • Updated dose proportionality assessment to be performed separately for each route rather than across routes.
Section 2.2 Study Objectives and Estimands	• Exploratory endpoint CCI [REDACTED] [REDACTED]
Section 10.2 Appendix 2: Schedule of Activities	• Update protocol defined schedule of events per protocol amendment 6.
Section 10.3: Assessment Windows	• Clarified that all assessments/events, including PK, will be assigned to assessment windows/analysis visits. • Analysis windows were updated to incorporate cohort 4b and 4h assessments and other minor corrections.

Section 10.4: Appendix 4: Study Phases, Study Periods, and Treatment Emergent Adverse Events	
 Added analysis period derivation details for CCI [REDACTED]
Section 10.6.3 Safety	
 CCI [REDACTED] CCI [REDACTED]
Section 10.10 Appendix 10: List of Data Displays	
 CCI [REDACTED] Added displays to summarize clinical chemistry, hematology, coagulation, ECG and vitals sign values (in addition to change from baseline) Updated analysis population to Safety – LA Exposure for ISR displays Updated delivery classifications (i.e., Cohort 1-5 IA, Cohort 1-5, EOS). Combined separate Part 1 and Part 2 displays into a single display. Additional programming notes added Updated presentation of treatment groups in the table shells document.
General	
 Minor editorial and document formatting revisions

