10.6. Appendix 6: Derived and Transformed Data

10.6.1. General

Multiple Measurements at One Analysis Time Point

 • For non-ECG assessments: 
 ○ If there are multiple measurements within a time window (per Section 10.3), the value closest to the target day for that window will be used. If values are the same distance from the target, then the mean of the measurements (for quantitative parameters) or the worst-case of the measurements (for qualitative parameters) will be calculated and used in any derivation of summary statistics. • For ECG assessments, the average value (for quantitative parameters) or the worst-case value (for interpretation) from the triplicate assessments will be calculated and used in all of the summary statistics. • Only planned assessment timepoints (according to Appendix 2: Schedule of Activities) will be included in data displays summarizing measurements by visit. • Measurements at timepoints not selected for summarization by visit will be included in worst-case post-baseline determinations and in data listings. 
 ○ Worst-case post-baseline determination, details are outlined in the Programming Notes from Appendix 10: List of Data Displays. • Participants having both High and Low values for Normal Ranges at any post-baseline visit for vital sign measurements in the relevant Potential Clinical Importance summary tables.
Study Day

 • Calculated as the number of days from First Dose Date of CAB: 
 • Ref Date = Missing → Study Day = Missing • Ref Date < First Dose Date of CAB → Study Day = Ref Date – First Dose Date of CAB • Ref Date ≥ First Dose Date of CAB → Study Day = Ref Date – (First Dose Date of CAB) + 1

Period Day

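### Cohort 4h's Day 3 and Day 5 safety labs have no analysis window of their own, so they are absorbed into Day 8 and drop out of the by-visit tables

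*SAP*

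**What the plan says.** Protocol Section 1.3.4 (Cohort 4h schedule), footnote 13, attached to the haematology, chemistry and urinalysis row, reads "No urinalysis needs to be performed on Days 3 and 5". It exempts only urinalysis, so haematology and chemistry are due on both days. The SAP's copy of the schedule in Appendix 2 carries the same footnote.

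SAP Section 10.3 assigns every assessment to a window "according to actual dates of collection rather than the nominal visit labels recorded on the eCRF or in the laboratory database". By-visit displays "will only report visits in which the parameter is a planned collection according to" the schedule.

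For Part 1, Injection 1, the lab rows of SAP Table 2 are:

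- Day 1
- "2 \leq \text{Injection 1 Period Day} \leq 11", labelled Day 8
- "12 \leq \text{Injection 1 Period Day} \leq 21", labelled Day 14
- Period Day 22 onward, labelled Week 4

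None of these rows is specific to Cohort 4h. Where a window holds several non-ECG values, SAP Section 10.6.1 says "the value closest to the target day for that window will be used"; a mean or worst case is taken only when values are equally distant. It adds: "Measurements at timepoints not selected for summarization by visit will be included in worst-case post-baseline determinations and in data listings".

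**The concern.** Two planned laboratory visits exist in the schedule but not in the window table. Their results go into a visit that already has its own draw, and the selection rule then sets them aside. The value and change-from-baseline tables for chemistry and haematology would show Cohort 4h at Day 8, Day 14 and Week 4, with nothing between the injection and Day 8. Protocol Section 2.3 describes this cohort as the first human administration of CAB with rHuPH20, so early laboratory data are of particular interest.

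There is also a labelling risk. Protocol Section 1.3.4, footnote 12, allows discharge from Day 5, with participants returning for later assessments. A missed Day 8 draw is therefore plausible, and a Day 5 value would then be presented as Day 8.

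**Working it through.** No sample-size formula applies. The check runs the scheduled lab days through the SAP's own rules.

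**Inputs**

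- Cohort 4h post-dose lab days to Week 4: Days 3 and 5 (footnote 13), and Days 8, 14 and 28 (schedule grid, matching the lab target days in SAP Table 2).
- Lab windows, Part 1 Injection 1 (SAP Table 2): Day 1; Days 2–11, target 8; Days 12–21, target 14; Day 22 onward, target 28.
- Selection rule (SAP Section 10.6.1): smallest |actual day − target day|.
- Cohort size: 20, as 10 + 10 (protocol synopsis).

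**Slotting under the plan**

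| Actual day | Window | Distance from target | Outcome |
|---|---|---|---|
| 3 | Day 8 | abs(3 − 8) = 5 | not summarised by visit |
| 5 | Day 8 | abs(5 − 8) = 3 | not summarised by visit |
| 8 | Day 8 | abs(8 − 8) = 0 | selected |
| 14 | Day 14 | 0 | selected |
| 28 | Week 4 | 0 | selected |

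Neither of two possible escapes works. The table's fallback for records that fit no window cannot apply, because Days 3 and 5 lie inside 2–11. The nominal visit label cannot help, because slotting is by actual date.

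**Size, complete data**

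- Draws set aside: 2 × 20 = 40.
- Draws falling in Days 2–11: 3 × 20 = 60, so 40 of 60 are not shown.
- Post-dose draws to Week 4: 5 × 20 = 100, so 40 of 100 are not shown.
- Lab visits summarised: 3 of 5.

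**Missing draws**

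- Day 8 missing: the candidates are Days 3 and 5, at distances 5 and 3. Day 5 is reported as Day 8 and Day 3 is set aside.
- Days 5 and 8 both missing: Day 3 is reported as Day 8.

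**Comparison within the SAP**

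Table 2 gives Cohort 4h its own ECG rows for Days 2 to 8 and Day 10, and a Day 4 PK row. Table 3 gives Part 2, which also has early labs, separate lab windows for Day 2, Days 3–4, Days 5–6 and Days 7–8. The missing Cohort 4h lab rows look like an omission rather than a choice.

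**Slotting with separate rows**

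With Days 2–4 as Day 3, Days 5–6 as Day 5 and Days 7–11 as Day 8, each of the five scheduled days maps to its own visit. Nothing is set aside, and 5 of 5 visits are summarised. If Day 8 is missed, it stays missing.

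**The case against.** The strongest answer is that little of safety consequence is lost. Values not selected still enter worst-case determinations, so they feed the maximum-grade tables (2.18 and 2.21). They should also feed the hepatobiliary table (2.34), whose programming note includes unscheduled visits. Listings 26 and 27 give all chemistry and haematology data for any participant with a toxicity. Participant protection does not depend on analysis windows: investigators review each laboratory report, the liver stopping criteria apply, and sentinel participants have a 10-day safety review. The documents give no stated reason for the Day 3 and Day 5 labs, and protocol Section 4.2.3 describes the effect of rHuPH20 as local to the injection site.

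All of that stands, and it keeps the point minor. It does not restore the two visits. The maximum-grade tables carry no timing, and the listings omit participants without a graded result. For example, ALT grading begins at 1.25 × ULN (SAP Section 10.8.1). A Day 3 rise below that level, in a participant with no other toxicity, would appear in no by-visit table and no planned lab listing. The group mean change on Days 3 and 5 would not be tabulated for anyone. The purpose of the extra draws is inferred; that they were planned is not.

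**Conclusion.** The plan is wrong as written on this point, at minor severity. Applied literally, SAP Table 2 and the closest-to-target rule remove Cohort 4h's Day 3 and Day 5 results from Tables 2.16, 2.17, 2.19 and 2.20, or relabel one of them as Day 8 when the Day 8 draw is absent.

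Forty draw sets is a ceiling that assumes all 20 participants have complete draws on the scheduled days. For any one participant, having both early draws set aside and having one relabelled are alternatives and do not add. The conclusion rests on footnote 13 for the lab days and on Table 2 as it stands. The PK endpoints, graded-toxicity summaries and real-time safety review are not affected.

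**What to change.** Add three Cohort 4h lab rows to SAP Table 2 for Injection 1, and state that the general Days 2–11 lab row does not apply to Cohort 4h, so that no record fits two windows:

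- Day 3: Period Days 2–4, target 3
- Day 5: Period Days 5–6, target 5
- Day 8: Period Days 7–11, target 8

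The exact cut-points are for the sponsor to set, provided the rows do not overlap and each scheduled day has its own visit. The cost is three window rows and two extra visits for one cohort in four tables. No new data collection is needed.
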